### **Other Exclusions:**

- The age range of the subjects will be limited to those between 21 and 80 years because the normal adaptive processes to aerobic exercise are generally less well understood in the childhood, adolescent, and aged subset of the population, and reference ranges for many of the exercise response variables are less well accepted than in the general adult subset. The age range of 21 to 80 encompasses the range generally referred to in the Inova Fairfax pulmonary rehabilitation program, which is one of the few pulmonary rehabilitation programs in existence serving patients who have advanced lung disease
- Subjects will not typically include individuals in Class I because patients are usually in Class II or III at the time of diagnosis.

- Subjects in NYHA Class IV will typically be excluded as the instability of their symptoms is a contraindication for exercise testing or training by nearly all published guidelines.
- Subjects in Class I may be included if they walk less than 400 meters during a six-minute walk test.
- Subjects in Class IV may be included if they are able to walk at least 50 meters during a six-minute walk test.
- Subjects with severe Raynaud’s phenomenon will be excluded from participation in the arterial occlusion muscle oxygenation capacity test.

**New York Heart Association Functional Classification**

Class	Patient Symptoms
Class I (Mild)	No limitation of physical activity. Ordinary physical activity does not cause undue fatigue, palpitation, or dyspnea (shortness of breath).
Class II (Mild)	Slight limitation of physical activity. Comfortable at rest, but ordinary physical activity results in fatigue, palpitation, or dyspnea.
Class III (Moderate)	Marked limitation of physical activity. Comfortable at rest, but less than ordinary activity causes fatigue, palpitation, or dyspnea.
Class IV (Severe)	Unable to carry out any physical activity without discomfort. Symptoms of cardiac insufficiency at rest. If any physical activity is undertaken, discomfort is increased.

**Monitoring Subjects and Criteria for Withdrawal from the Study:** Subjects will be followed carefully during the study. At the start of each study day, subjects will be asked whether they are experiencing any unusual symptoms, and vital signs will be measured (pulse rate, oxygen saturation, resting blood pressure). All subjects will undergo EKG and echocardiography before and during the symptom limited exercise test. We will monitor heart function in the rehabilitation medicine exercise lab during exercise, and stop the exercise if there are any signs of heart problems.

Subjects enrolled who subsequently meet the exclusion criteria above at any time during the protocol will be excluded (off-study exclusion criteria).

[name], as the Principal Investigator, will make the decision to include or exclude potential participants based on their meeting inclusion, exclusion or off-study exclusion criteria.

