## Informational Gaps

Outcomes of our preliminary study suggest the value of aerobic training for increasing cardiorespiratory capacity, diminishing fatigue severity, and improving the capacity for performing physical activities in patients with ILD. Increased cardiorespiratory function appears to mediate improvements in PWC, fatigue severity, and physical activity. However the cardiorespiratory adaptation results are somewhat atypical. In many conditions, peak  $\text{VO}_2$  is 15-20% higher after training. This occurs as a result of increases in both central circulatory  $\text{O}_2$  delivery and peripheral  $\text{O}_2$  extraction. In our study of patients with ILD, peak  $\text{VO}_2$  increased only by 4.6% after AET despite a 16.3% increase in peak a- $\text{vO}_2$ . An increase in peak  $\text{Qt}$  was not observed. Resting right ventricular function was within normal ranges,  $\text{Qt}$  increased during exercise, and patients did not become symptomatic of congestive heart failure. Therefore the mechanisms limiting the improvement in peak  $\text{VO}_2$  were likely impaired pulmonary gas exchange and restricted lung function, which are hallmarks of the ILD clinical course.

The mechanistic link to improvement provides relatively strong evidence for a substantial benefit of AET. However, some of the measurements, such as those made at volitional exhaustion, 6MWT distance and questionnaire responses could have been to some degree influenced by motivational factors and familiarity with the testing procedures. Therefore, a RCT is needed before the mechanistic and clinical effects of AET can be determined with confidence. We are proposing a small, phase 2 RCT to establish the safety and efficacy of AET in patients with ILD.

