## Research Objectives:

The objectives of the work proposed are, in patients who have ILD, to:

1. Determine the safety and tolerability of exercise training in patients with ILD to determine appropriate pulmonary rehabilitation exercise guidelines.
2. Examine responses and adaptations to exercise at quantifiable target intensities that correspond to energy expenditure requirements.
3. Understand changes in the symptom limited exercise test results, using training-specific testing modalities.
4. Examine the effects of exercise training on physical activity functioning.
5. Determine the relationships between patient's ability to achieve and maintain an aerobic steady state and to sustain physical activity.
6. Determine the effect of aerobic exercise training on psychosocial and behavioral functioning and other HRQOL components.
7. Based on the progression in training volume, delineate the time course of improvement in work capacity across an aerobic exercise training program.
8. Explore the relationships among measures of aerobic metabolic function and potential mechanistic factors that may limit oxidative metabolism.
9. Examine the relationships among indices of aerobic metabolic function and the mechanisms by which aerobic exercise training improves oxidative metabolism.

[figure not shown]
To accomplish these objectives, we will perform a RCT comparing a 10-week, interventional regimen of AET plus patient education (AET+) to a control condition of patient education only (CON) that does not include AET. A secondary study will also be conducted using a single "crossover" design in which the patients randomized to the control arm of the main study will receive AET after they are finished the 10-week education only regimen.

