## Study Design and Methods

### Overview of the Research Paradigm

### 1-year Follow-up

Patients will be contacted monthly for 1 year following completion of exercise training to determine continued exercise habits, the amount of re-hospitalizations, acceptance to a lung transplant waiting list, and mortality rate.

To qualify for participation, subjects will undergo physical evaluation by a credentialed member of the Rehabilitation Medicine Department's medical staff to determine if they meet the inclusion and exclusion criteria. At this time, subjects must answer "no" to the question "do you currently participate, or within the past six months have you regularly participated, in a structured exercise program greater than 30 minutes a day for 3 or more days a week." Subjects answering "no" to this question, and meeting other inclusion/exclusion criteria will then undergo an EKG and Doppler echocardiography to rule out pulmonary hypertension and right and left ventricular dysfunction. In addition, they will have pulmonary function testing with DLCO to rule out COPD and to assess lung diffusion capacity. Subjects will also undergo a blood draw for two tests: Nt ProBNP and Complete Blood Cell Count with Differential. Qualified participants will then receive the baseline research test battery, which includes 6MWT, tCPET with cardiac output and muscle oxygenation measurements, and questionnaires to measure patient-reported fatigue severity, physical activity, and other HRQoL domains.

After completion of the baseline research test battery, subjects will be randomized to one of two groups. The randomization design will be a 2x2 block randomization in which subjects will be randomized in pairs. The first subject will be assigned to either a control group that receives 10-weeks of patient education lectures (1 day per week, 1 hour each lecture) with no AET or an intervention group participating in AET, 3 days per week for 10 weeks, in addition to the educational lectures (AET+). The second subject of the pair will be assigned to the opposite group.

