- Profile of Mood States (POMS): The Profile of Mood States (POMS) measures present mood state by a list of adjectives. POMS measures six dimensions of affect or mood, including tension-anxiety, depression-dejection, anger-hostility, vigor-activity, fatigue-inertia, and confusion-bewilderment.
- King's Brief Interstitial Lung Disease Health Status Questionnaire (K-BILD): The K-BILD is designed to measure health status in patients with interstitial lung disease through three domains (breathlessness and activities, chest symptoms, and psychological). The questionnaire has 15 items in total.

Randomization: Once the subjects have completed baseline testing they will be randomized to one of the two conditions: AET+ or CON. We will use block randomization to keep groups as equal in number as possible and to avoid early filling of one of the groups. An independent randomizer ([name], P.T., Ph.D., RMD, Epidemiology and Biostatistics Section) who is not affiliated with this study in any other way, will perform randomization of subjects. The AET+ and CON procedures will occur in the Clinical Center at The National Institutes of Health. The education regimen will be conducted at separate times for the AET+ and CON groups to avoid cross contamination.

**Educational Sessions:** The education portion is comprised of 13 separate lectures. Subjects in the AET+ arm will receive 1-2 lectures per week as needed following their exercise session to fulfill the education requirement within 10 weeks. Subjects in the CON arm will receive the 13 lectures within the 10-week education period. Many classes will take more than one class session to cover the material. For example, inhaler use/lung medications will require at least 2 sessions to cover.

The lectures will include the following topics:

- Lung Anatomy/Physiology/Breathing Retraining
- Lung Diseases and Medications Part 1
- Lung Diseases and Medications Part 2
- Oxygen Therapy/Sleep Disorders
- Preventing Infection/Airway Clearance
- Diagnostic Testing
- Advance Care Planning/Energy Conversation
- Emotional/Social Well Being
- Panic Control/Relaxation
- Nutrition/Fall Prevention
- Benefits of Exercise/Disease Management/Community Resources
- Home Recommendations (excluding exercise recommendations)

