**If the NIH Study Coordinator interviews a potential subject from any source the following script will be followed:**

“Thank you for your interest regarding the research we are conducting to determine the benefits of a walking program for patients with interstitial lung disease. We are accepting volunteers between the ages of 21 and 80 who have been diagnosed with interstitial lung disease and who have been referred by their physician for pulmonary rehabilitation. If you are enrolled in the study we would ask that you come to NIH for a day of testing which would include a test to determine how far you can walk in 6 minutes, breathing tests and a treadmill exercise test. During the treadmill test you will have 16 electrodes on your chest, we will ask that you wear a neoprene mask to collect data on the amount of oxygen you breathe in and out, as well an electrode on your calf to determine the amount of oxygen your muscle utilizes for energy.

After testing you will be randomized into one of two groups, group 1 will receive exercise and education simultaneously 3 days a week for 10 weeks concluding with repeat testing at NIH. Group 2 is a 20 week group where you will receive education one day each week for 10 weeks, return to NIH for testing followed by 10 weeks of exercise 3 days a week and finally one last testing session at NIH. We do not have control over which group you are assigned to. You will be put into a group by a process called “randomization” where you have a 50-50 chance of landing in either group. Does this sound like something that you would like to participate in?”

If they answer “yes,” we ask if they have time to answer a short questionnaire that would allow us to evaluate their eligibility and safety for inclusion into the study. (Please see Appendix 2 of the protocol to compare the inclusion/exclusion criteria with the questions we would be asking.)

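### Symptoms are not sought on a matched schedule in AET+ and CON, so a by-arm count of short, non-serious events would partly reflect attendance

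*Combined protocol and SAP*

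**What the plan says.** Objective 1 under Research Objectives is to "Determine the safety and tolerability of exercise training in patients with ILD to determine appropriate pulmonary rehabilitation exercise guidelines". The same section continues: "To accomplish these objectives, we will perform a RCT comparing a 10-week, interventional regimen of AET plus patient education (AET+) to a control condition". Informational Gaps states the purpose as "We are proposing a small, phase 2 RCT to establish the safety and efficacy of AET in patients with ILD".

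Routine symptom enquiry appears once, in the paragraph headed Monitoring Subjects and Criteria for Withdrawal from the Study, which reads: "At the start of each study day, subjects will be asked whether they are experiencing any unusual symptoms, and vital signs will be measured". The term study day is not defined and no look-back period is given.

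Attendance differs by design. The Overview of the Research Paradigm gives CON "10-weeks of patient education lectures (1 day per week, 1 hour each lecture" and describes AET+ as "an intervention group participating in AET, 3 days per week for 10 weeks, in addition to the educational lectures". The recruitment script tells prospective CON patients that "you will receive education one day each week for 10 weeks". Educational Sessions adds "Subjects in the CON arm will receive the 13 lectures within the 10-week education period", notes that many classes need more than one session, and places AET+ lectures after exercise sessions. Exercise Training sets minimum attendance at 24 sessions.

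The Analysis section names dependent variables for Aims 1 to 3, the crossover and Aim 4. Adverse events are not among them. Echocardiography and lung function are repeated in both arms after the 10-week regimen, but are not named there either.

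**The concern.** A comparison of adverse events between arms is fair only if both arms had the same chance of having an event recorded. Here the opportunity to report follows attendance, and attendance is part of the treatment difference. A brief symptom that comes and goes between CON lectures may never be recorded, while the same symptom in AET+ is likely to coincide with a session.

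Two errors become possible when Objective 1 is reported or when the biostatistics group examines interim results. An excess in AET+ may come only from the schedule, or a real excess may be dismissed as an artefact of it. Objective 1 is meant to inform exercise guidelines, so either error would matter. The crossover does not help, because CON moves from one day a week to three when it starts training.

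**Working it through.** The documents give no figure for safety, so there is none to reproduce.

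**1. Opportunities to record a symptom in the randomised 10 weeks**

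- AET+: 3 × 10 = 30 scheduled, 24 at minimum attendance. Lectures add no separate days.
- CON: 1 × 10 = 10, or 13 if each lecture has its own day, and possibly more because some classes need extra sessions.
- Ratios: 30/10 = 3.0 and 24/13 = 1.85. The second is not a floor.
- If study day means NIH test days only: baseline and week 10 in each arm, 2 against 2. Staff contact during the 10 weeks remains 24 to 30 days against about 10 to 13 or more.

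**2. Share of episodes recorded, by duration**

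Assume an episode starts on a random day, lasts D days, and is recorded only if present on an asked day. AET+ asking days are assumed to be 2, 2 and 3 days apart, and CON asking days 7 apart.

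Share in AET+ = [min(D,2) + min(D,2) + min(D,3)]/7. Share in CON = min(D,7)/7.

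| D (days) | AET+ | CON | Ratio |
|---|---|---|---|
| 1 | 3/7 | 1/7 | 3.0 |
| 2 | 6/7 | 2/7 | 3.0 |
| 3 | 7/7 | 3/7 | 2.3 |
| 4 | 7/7 | 4/7 | 1.75 |
| 5 | 7/7 | 5/7 | 1.4 |
| 7 or more | 7/7 | 7/7 | 1.0 |

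Spontaneous recall of the past few days acts like a longer D. With 7 days of recall the imbalance disappears.

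**3. Effect on a by-arm count, if one were tested**

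Let L be the mean number of episodes per patient in 10 weeks, the same in both arms, with Poisson counts. The share of patients with at least one recorded episode is 1 − exp(−L × capture share). At L = 1:

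- D = 1: 1 − exp(−3/7) = 34.9% against 1 − exp(−1/7) = 13.3%.
- D = 2: 57.6% against 24.9%.
- D = 4: 63.2% against 43.5%.

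Exact probability that a two-sided Fisher test gives p ≤ 0.05 with 30 per arm, although true rates are equal (30 against 10 contacts):

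| L | D = 1 | D = 2 | D = 4 |
|---|---|---|---|
| 0.1 | 0.1% | 1.5% | 1.3% |
| 0.2 | 1.5% | 9.8% | 5.5% |
| 0.5 | 15.2% | 39.2% | 15.2% |
| 1 | 39.2% | 65.3% | 24.9% |
| 2 | 65.3% | 82.9% | 29.0% |

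At 24 against 13 contacts and L = 1, taking the capture share as days × D/70 capped at 1, the figures are 12.5%, 22.4% and 8.5%. If both arms had the AET+ schedule, the figure would be at most about 3%.

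L, D and the weekly pattern are assumptions; the documents supply none of them. Benefits and Risks/Discomforts mentions fatigue of up to 24 hours and soreness subsiding within seven days. Those are symptoms caused by exercise, so they cannot calibrate a model with equal rates in the two arms.

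**The case against.** **Study day may mean NIH test day.** The sentences after the symptom question concern the exercise test and the exercise laboratory, so this reading is plausible. A reader might take 30 against 10 as settled, and the text does not support that. What remains is that either reading leaves the arms unmatched over the 10 weeks. Under the narrow one there is no systematic enquiry between baseline and week 10, and events come from what staff happen to see or hear, on unequal days.

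**Objective 1 may not be a between-arm question.** Several of the nine objectives can be studied only within trained patients, and tolerability of training is partly one of them. This stands for tolerability. It does not remove the protocol's statement that its objectives, safety included, are met by comparing the two regimens.

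**Nobody plans the test.** Safety oversight is by case: a single study-related death, infarction or stroke prompts consideration of stopping, and a medical monitor reviews events. This is correct. A reader might infer that the trial runs a 39% or 65% risk of a false safety signal. The documents do not support that, because those figures need an unsourced event rate and an unplanned test.

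**Other reporting routes exist.** Medication changes must be reported within one week in both arms, which would pick up events that lead to treatment. Brief untreated symptoms would still be missed.

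**Echo and lung function.** A reader might see their absence from the Analysis section as an error. They are introduced as eligibility tests and no hypothesis concerns them, so summarising them by arm is an optional addition.

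**Conclusion.** The point holds in a limited form. Safety is an objective of a randomised comparison, yet nothing in the monitoring, event-reporting or Analysis sections equalises the recording of short, non-serious symptoms between arms or adjusts for the difference.

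The distortion is bounded: up to 3:1 for episodes of 1 to 2 days, falling to 1:1 at 7 days or longer. The chance of a false significant difference runs from about 0 to 2% at 0.1 episodes per patient to about 65% at 1 per patient with 30 against 10 contacts. It depends wholly on the assumed rate, duration and schedule.

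It would be wrong to conclude that the efficacy findings are compromised. The 6-minute walk outcome, its power and the Aim 1 to 3 measures are collected on the same schedule in both arms. Deaths and hospital stays should come to light in either arm. Severity is minor to moderate.

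**What to change.** 1. Define study day.
2. Ask both arms the same symptom and event checklist once a week, covering the past 7 days: on CON's education day and at one named AET+ session, and again at the week-10 visit. Base the by-arm safety comparison on these answers only. Keep asking at every session for patient safety, and list those reports separately.
3. Add to the Analysis section a descriptive table by arm for the randomised 10 weeks: serious adverse events, events from the matched checklist, and withdrawals. Give exact limits; for example, 0 events in 30 patients has an upper 95% limit of 1 − 0.025^(1/30) = 11.6%.
4. Optionally, summarise week-10 echocardiography and lung function by arm. NT-proBNP can be added if it is drawn in CON at week 10, which the follow-up battery does not make clear.

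The cost is a short form on days patients already attend, one paragraph and one table, with no extra visits or patients. For patients already treated, AET+ reports can be restricted to one session a week, but the 7-day recall cannot be recovered. The drawbacks are that some AET+ reports fall outside the arm comparison, and that the wide intervals must not be read as showing no harm.

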**Principal Investigator:**

[name], MPH (E) \*  
Chief, NIH Clinical Center, Rehabilitation Medicine Department  
[contact] [contact]  
[name]

**Estimated Duration of Study:** 36-60 Months

**Estimated Completion Date of Study:** December 2021

Subjects of study:	Number	Sex	Age range
	60	M&F	21-80 years

60 subjects with Interstitial Lung Disease without Pulmonary Hypertension. Enrollment will remain open until 30 subjects in the Aerobic Exercise Training (AET) group and 30 subjects in the Control (CON) have completed the study.

**Project involves ionizing radiation?** No

**Offsite project?** Yes

**Multi-Institutional project?** Yes, NIH (medical and research testing, and exercise and educational training), Inova Fairfax Hospital (exercise and educational training),

**DSMB involvement?** No

**Tech Transfer: CRADA, MTA** No

**Identifying Words:** Exercise, Interstitial Lung Disease, Pulmonary Rehabilitation

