After completion of the AET+ or control regimens, subjects will undergo the follow up research test battery. The follow up battery consists of echocardiogram, pulmonary function test, arterial occlusion muscle oxygenation test, 6MWT, tCPET, and questionnaires identical to those included in the battery at baseline. Subjects in the control group will subsequently participate in a 10-week AET regimen identical to AET+ except without the educational lectures, since participation in the lectures was completed as the control condition. A second identical, follow up test battery will be completed by this group after the crossover AET regimen is completed. After completion of their AET+, subjects will be contacted monthly with regard to continued exercise habits, the frequency, length, and severity of hospitalizations, or acceptance to a lung transplant waiting list. Mortality will also be assessed at this time.

**Specific Aim 1:** "Determination of the Influence of AET+ on PWC in Patients with ILD".

The main outcome variable for this project is 6MWT distance, which is the most frequently used measure of physical performance for evaluating patients with ILD and other advanced lung diseases. A minimal clinically important difference (MCID) for 6MWT distance has been determined to be approximately 30 meters in ILD. Additional measures of PWC used in this study are peak WR on the tCPET, and performance and perceived fatigability as measured by a modification of the method used by Schnelle and coworkers in an older cohort. We will measure all 4 of these variables at baseline and after the AET+ and control regimens, as well as after the crossover regimen. We hypothesize that:

- 1.1. An increase in 6MWT distance of at least 30 meters longer than control will be observed after AET+.
- 1.2. A significant increase in peak WR will be observed after AET+ compared to control.
- 1.3. A significant decrease in performance fatigability will be observed after AET+ compared to control.
- 1.4. A significant decrease in perceived fatigability will be observed after AET+ compared to control.

- 1.5 In the Sub-study on Crossover we hypothesize that AET will result in improvements over baseline in all of the variables of interest including 6MWT, peak WR, and performance and perceived fatigability that are similar to AET+.

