range of correlation under consideration at each level of improvement in 6MWT distance. The observed effect sizes were 0.16-0.17 at 25 m, 0.18-0.20 at 30 m, 0.21-0.23 at 35 m, and 0.24-0.265 at 40 m. As we expect to have underestimated correlation, even at the given improvement levels the predicted effect sizes are highly conservative. With either correlation modestly above 0.40 and 30 m improvement, correlation of 0.25 and 35 m improvement, or some point in between these two at a sample size of  $n=60$  the simulated effect sizes predict a power above 80% at a significance level of 0.05. Modestly higher improvement, in the range of 35-38 m, and correlation of 0.38-0.45 will result in the study having a power of approximately 95%. This range is compatible with the observed effect sizes in the literature in the moderate to large range, using Cohen's conventions for effect sizes where these ranges are 0.25-0.4 for ANOVA and 0.5-0.8 for t-tests.

To support the results from simulation, we finish by observing how power is maintained at a slightly less conservative estimate of effect size and correlation but under the additional assumption of significant subject withdrawal from the study. Assuming an effect size of 0.25 and test-retest correlation of 0.40 then a minimum of 33 patients in each group are necessary to achieve the desired power of 0.95. Even then, if only 20 patients complete the protocol in each group post-hoc analysis predicts a not-unacceptable power of 0.803.

Our recruitment goal was therefore set at 60 patients, however, completion rates to date for this study suggest that 80 subjects may need to be consented and screened in order to achieve 60 completed subjects. Therefore, the enrollment goal remains the same at 60 patients in total (30 in each group) over the course of the study as it ensures high power for comparison of 6MWT distance between AET+ and CON groups, with a buffer for moderate patient dropout. However, recruitment will remain open until 30 subjects in each of the AET+ and CON cohorts have completed the entire protocol.

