Based on this recruitment goal we have agreed upon the following strategy to maintain an effective end power. At which point we attain 45 completed subjects (total) an analysis of the standard deviations in 6MWD from pre to post will be determined in the control and intervention cohorts. To maintain the blinding controls of the study as much as possible, this analysis will be performed by our statistician only. Based on this analysis our sample size will be adjusted thereafter to reflect a more accurate sample size needed to maintain an effective end power.

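### The off-study rule continues after randomisation and the plan states no all-randomised analysis, so the primary 6MWD comparison is exposed to outcome-related loss

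*Combined protocol and SAP*

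**What the plan says.** **The rule.** Under Monitoring Subjects and Criteria for Withdrawal from the Study: "Subjects enrolled who subsequently meet the exclusion criteria above at any time during the protocol will be excluded (off-study exclusion criteria". The next sentence says that the principal investigator "will make the decision to include or exclude potential participants based on their meeting inclusion, exclusion or off-study exclusion criteria".

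**Its reach.** Randomisation follows baseline testing (Overview of the Research Paradigm; Randomization), so the whole 10-week comparison falls under the rule. The Data and Safety Monitoring Plan says that study personnel cannot stay blinded once subjects are randomised.

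**The criteria.** Many entries under Exclusion Criteria have nothing to do with ILD progression. Four can reflect worsening: failure to hold resting saturation on oxygen, acute cor pulmonale, acceptance for transplant listing, and medical complications judged by the investigator.

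**Follow-up and recruitment.** The Overview places the follow-up test battery, including the 6MWT, after completion of the assigned regimen. The front page says "Enrollment will remain open until 30 subjects in the Aerobic Exercise Training (AET) group and 30 subjects in the Control (CON) have completed", and Sample Size says "recruitment will remain open until 30 subjects in each of the AET+ and CON cohorts have completed the entire protocol". Sample Size also expects that "80 subjects may need to be consented and screened in order to achieve 60 completed subjects".

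**Analysis.** The Analysis section specifies a 2-way mixed model ANOVA, or ANCOVA if baseline differs. It defines no analysis population and gives no rule for a subject without a 10-week 6MWD.

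**The concern.** Randomisation protects the comparison only while outcomes are collected and analysed for the subjects who were randomised. Here a stated rule can remove subjects afterwards, partly for reasons likely to go with a shorter walk, on the decision of someone who can know the allocation. Because the 6MWT is tied to completing the regimen, following the plan as written leaves no 10-week value for a removed subject, and recruitment then continues until enough others complete.

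Equal removal cannot be presumed. Symptoms and saturation are checked at the start of each study day. If that includes attendance days, AET+ is seen three days a week and CON one day a week, so the same deterioration may be detected more often in one arm.

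If removal is related to worsening and differs between arms, the remaining subjects are no longer a randomised comparison. A 6MWT that was never done cannot be recovered at analysis.

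**Working it through.** **1. The plan's own figures.** Sample Size gives 33 per group for power 0.95 at f = 0.25 and correlation 0.40, and power 0.803 with 20 per group. For the classical repeated-measures interaction F test, the noncentrality is f² × N × 2 / (1 − ρ), with df (1, N − 2) and alpha 0.05:
- N = 66: 0.0625 × 66 × 2 / 0.60 = 13.75, power 0.955 (N = 64 gives 0.949)
- N = 40: 0.0625 × 40 × 2 / 0.60 = 8.33, power 0.803

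Both reproduce. This shows which test was used for planning and that dropout was considered only as a loss of power. It does not endorse the effect size.

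**2. Attrition.** (80 − 60) / 80 = 25%. This counts from consent and screening, so it includes screen failures and is an upper bound for loss after randomisation. It is not split by arm.

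**3. Shift from analysing completers.** If a share p of an arm is removed and those subjects' mean change is worse than that of completers by a gap g, the completers' mean exceeds the arm's all-randomised mean by p × g. The treatment contrast shifts by p(AET+) × g(AET+) − p(CON) × g(CON). With equal shares and equal gaps, or gaps of zero, the shift is 0. The sign depends on which arm loses more.

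**4. Illustration.** The gap is an assumption of 26 to 50 m. These are the 24-week declines in idiopathic pulmonary fibrosis cited in Background, borrowed for scale only; the trial window is 10 weeks in mixed ILD. Let 30 subjects complete in the affected arm, with k net extra removals there and none in the other arm. The shift is k / (30 + k) × g. Setting it to 5 m gives k = 150 / (g − 5):
- g = 50: 150 / 45 = 3.3, so 4 removals (4/34 × 50 = 5.9 m)
- g = 26: 150 / 21 = 7.1, so 8 removals (8/38 × 26 = 5.5 m)

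A 5 m shift is 5 / 30 = 17% of the 30 m target.

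**5. Against sampling error.** With SD 127 m (Sample Size), the SD of change is 127 × √(2(1 − ρ)): 139.1 m at ρ = 0.40 and 71.8 m at the preliminary study's 0.84. With 30 per arm, the standard error is this × √(2/30): 35.9 m and 18.5 m. A 5 m shift is 0.14 to 0.27 standard errors.

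**6. An outer case, not an estimate.** Suppose that all 80 were randomised, 40 per arm, that 10 per arm were lost, and that only the AET+ losses were related to outcome. The shift is 0.25 × 26 = 6.5 m to 0.25 × 50 = 12.5 m. In 20,000 simulated trials with no true effect (t test on change), the two-sided rejection rate was about 0.05 to 0.07 at ρ = 0.40 and 0.06 to 0.10 at ρ = 0.84, against a nominal 0.05.

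**The case against.** The best reply is that the rule takes people off study without saying that their data are discarded, and that lines about completion set when recruitment stops, not who is analysed. That is right. A reader might infer that the plan prescribes a completer analysis, or that the result will be biased; the documents support neither. They leave the analysis set open.

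A mixed model fitted by likelihood would keep subjects who have only a baseline value and would be valid under missing at random. The plan does not say that this is what it intends, and a classical two-time-point ANOVA drops such subjects. Even a likelihood fit does not help if loss depends on the unseen 10-week result.

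Much of the rule operates harmlessly before randomisation, because consent precedes the screening tests. Subjects who newly need oxygen during training stay in (Exercise Training). The sentence on the investigator's decision speaks of potential participants, although it also names the off-study criteria. An independent medical monitor is apprised of significant adverse events. These points narrow the exposure but do not close it.

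Three further inferences are tempting and should not be drawn:

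- **Controls lost during crossover.** The script says "Group 2 is a 20 week group where you will receive education one day each week for 10 weeks", and the Overview adds that "Subjects in the control group will subsequently participate in a 10-week AET regimen identical to AET+ except without the educational lectures". One might conclude that a control removed in weeks 11 to 20 drops out of the primary comparison. But the 6MWT section defines the outcome as change over the assigned regimen, and Analysis treats the crossover as a separate sub-study. Nothing there removes that control's 10-week value.
- **The interim SD review.** "At which point we attain 45 completed subjects (total) an analysis of the standard deviations in 6MWD" ties that review to completers. It is not a separate bias mechanism for the treatment comparison.
- **Transplant listing.** It is both an off-study criterion and an Aim 4 outcome. Aim 4 counts it in the year after the main study, so this is a contradiction only if the protocol period is read to include that year.

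**Conclusion.** The point holds as an exposure of the primary comparison. A stated rule, not only a silence, allows removal after randomisation for reasons that can go with a worse outcome. The schedule does not call for the 10-week test in those removed, and no all-randomised analysis is stated.

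The size and direction of any bias cannot be determined, because neither removals by arm nor the outcomes of removed subjects are given. On the assumed 26 to 50 m gap, with 30 completing in the affected arm, about 4 to 8 net extra removals in one arm would shift the estimate by 5 m. That is modest beside the sampling error. It is still worth correcting, because the protection is cheap and must be in place before the tests are missed. Confidence is medium.

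**What to change.** This is a cheap improvement, mainly to wording:

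1. State that meeting an off-study criterion does not by itself end outcome collection, and that the 10-week 6MWT is sought from every randomised subject where the investigator judges it safe. This matters most, because only collected outcomes show whether the loss was selective.
2. Make the primary analysis all randomised subjects in their assigned arm, using every available 10-week 6MWD with baseline 6MWD in the model. Report removals by arm and reason.
3. Add a sensitivity analysis that assigns unfavourable values to subjects lost to deterioration or death, and show completers as supportive. A likelihood model or imputation from baseline 6MWD alone is not enough: with one baseline and one follow-up, a subject without follow-up adds no information on how removed subjects changed, so outcome-related loss goes uncorrected.

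The cost is a few extra walk tests, modest analysis work, and possibly a less favourable estimate than completers would give. The stated sample size and power figures do not change. Who stops training remains the sponsor's clinical decision.
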